3.7. Type of Research

In this study, the reliability and effectiveness of our EyeCheckup software will be measured. Therefore, the study will be carried out as Medical Device Research (Excluding Thesis and Academic Studies) Without CE Mark, as determined by TITCK.

3.8. Research Population

All adult patients (male-female) aged 18 years and over who were diagnosed with diabetes but not diagnosed with diabetic retinopathy by the endocrinology outpatient clinic.

3.9. Inclusion Criteria for Volunteers

Fundus images of 900 volunteer patients with evaluable quality, with or without pathology, who applied to Akdeniz University Endocrinology and Metabolism Diseases Department with the diagnosis of diabetes, who were not diagnosed with Diabetic Retinopathy before and whose images can be taken from the posterior polar region of the eye with a fundus camera, will be included in the study.

- Diabetes must have been diagnosed
- Diabetic Retinopathy must not be diagnosed yet,
- The participant must understand the study and have signed informed consent,
- No history of any other retinal vascular disease, cataract, or other diseases that may affect the appearance of the retina or optic disc (refractive defect and ocular surface disease are allowed),
- No history of intraocular surgery other than cataract surgery, ocular laser therapy for any retinal disease, or ocular injection for diabetic macular edema or proliferative disease,
- No ambient blur preventing good retina photography
- Persons aged 18 and over are included in the study.

If at least one of these conditions is not met, the participant is not included in the study.

[one] Inan, UU, F. Ozturk, and SS Ermis, Pharmacologic pupil dilation in diabetic patients. Retina, 2003. 23(2): p. 254-6

3.10. Exclusion Criteria for Volunteers

Fundus images that have corneal or lens opacification that will prevent imaging, and that are not evaluable due to intravitreal hemorrhage or vitreous will not be included in the study. Patients followed or treated for DR will not be included in the study.

- If the volunteer are not diagnosed with diabetes,
- If the potential participant cannot understand the study or informed consent,
- If the volunteer has a history of retinal vascular disease other than diabetic retinopathy, glaucoma, or any other disease that may affect the appearance of the retina or optic disc.
- If the volunteer have had previous intraocular surgery including than cataract, laser intervention on the retina, or previous intraocular intervention for the treatment of diabetic retinopathy,
- If there is a permanent visual impairment in one or both eyes,
- If under the age of 18,

- If the participant is contraindicated for imaging with the fundus imaging systems used in the study,
- Exclude if there is an ambient blur in both eyes severe enough to impede good retinal photography.

If at least one of the above conditions is present, the participant is not included in the study.

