3.4. Rationale / Importance and Contribution of the Research

EyeCheckup is an automated software instrument designed to analyze digital color photographs of the ocular fundus to quickly screen for diabetic retinopathy (DR).

The main purpose of the study was to detect the presence of mild diabetic retinopathy or sight-threatening diabetic retinopathy from retinal fundus images in adult patients who applied to the endocrinology outpatient clinic due to diabetes, to grade and to determine the sensitivity and specificity of diabetic retinopathy, and to identify and classify the images with the developed

artificial intelligence algorithm. It is a comparison of diagnosis done by artificially intelligent algorithms and classification of DR done by doctors.

The primary efficacy endpoint in the study was that EyeCheckup's intended image capture workflow could be successfully used in conjunction with the EyeCheckup device to diagnose 80% or more of the participants for more than mild diabetic retinopathy (mtmDR) and vision-threatening diabetic retinopathy (vtDR) separately with a minimum 90% sensitivity and 90% specificity.

The secondary efficacy endpoint in the study was

Additional non-primary analyzes will also be performed to assess the following general conditions:

- Positive Predictive Value of EyeCheckup test for mtmDR and vtDR,
- Negative Predictive Value EyeCheckup test for mtmDR and vtDR.
- Positive and negative odds ratios for mtmDR and vtDR.

The study will include approximately 900 people with diabetes, excluding exclusions. They will be recruited voluntarily through 1 clinical center. Two photographs of the ocular fundus (one optic disc centered, one macula centered) will be obtained per eye using a non-mydriatic eye fundus camera from both eyes of the participants. These images will be analyzed by EyeCheckup. Then, pupil dilation will be achieved by instilling Tropicamide drops in both eyes of the patient and 4 quadrant photographs of both eyes will be taken with a fundus camera. Ophthalmologists will then evaluate and record the condition of the eyes based on images obtained with pupil dilation.

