3.5. Success Criteria of Study

Three different doctors will evaluate the volunteer's fundus images taken from fundus cameras and will make a decision about the presence of DR: Not more than Mild DR, More than mild DR (mtmDR), and Vision-threatening DR (vtDR). Decisions will be made by majority vote. The doctors' decision will be Ground Truth for us.

EyeCheckup will decide for both eyes of each volunteer. If it is the same as the doctors' decision, this decision will be considered correct.

Total correct number / Total number of eyes = Success rate

Our criteria for successful completion of the clinical trial: Success rate > 90%

EC-2021DR-TR DETECTION AND CLASSIFICATION OF DIABETIC RETINOPATHY FROM POSTERIOR POLE IMAGES WITH A DEEP LEARNING MODEL

At the same time, the Specificity and Sensitivity values should be calculated separately for mtmDR and vtDR and each should be above 90%.

Eye doctors (Normal, mtmDR, vtDR) make their decisions according to the ETDRS guidelines. Main signs to check for: Microaneurysms, Intreretinal hemorrhages (Intraretinal hemorrhage), Venous beading, IRMA, Neovascularization, Intravitreal hemorrhage, Preretinal hemorrhage

3.6. The benefit of the Research, Possible risks and precautions to be taken against harm:

Benefits;

According to the 2018 data from the World Health Organization, 285 million people worldwide have a visual impairment. It is known that more than 80% of all visual disorders can be prevented or treated. The retinal examination should be performed by an ophthalmologist and/or retinal specialist in order to prevent retinal-related visual disorders by making an accurate diagnosis, but people only consult an ophthalmologist when they feel any discomfort. Typically, by the time symptoms appear, the disease has reached advanced stages and requires a variety of expensive medical and surgical treatments. Unfortunately, at this stage, the disease often results in severe and permanent visual impairment and vision loss.

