3.11. Withdrawal of Volunteers from the Study - Exclusion Criteria

The volunteer may withdraw from this study at any time without giving any reason, provided that the principal investigator/doctor is informed. He assumes no liability for his refusal or subsequent withdrawal from this study, and this does not in any way affect the medical care that the patient needs now or in the future.

The researcher/doctor or the supporting organization, who is the coordinator of the study, may exclude the subject from the study without the consent of the subject, due to their negligence in fulfilling the requirements of the study program or in order to improve the quality of the medical care received by the patient. Fundus images that have corneal or lens opacification that will prevent imaging, and that are not evaluable due to intravitreal hemorrhage or vitreous will not be included in the study. Patients already diagnosed with DR will not be included in the study.

[figure not shown]
Participants withdrawing from the study for a serious or non-serious ACE should be monitored by the investigator until the clinical outcome of the ADE is determined. Any participant experiencing an ADE may withdraw from the study at any time at the discretion of the investigator. ADE(s) should be noted with appropriate ORFs and participant progress should be monitored until the ADE is resolved. The medical monitor or project manager should be informed.

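### Removing images made unreadable by intravitreal hemorrhage (3.10, 3.11) can take probable target-positive eyes out of the vtDR sensitivity, with no rule to count or bound them

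*Combined protocol and SAP*

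**What the plan says.** Section 3.10 states that fundus images "that are not evaluable due to intravitreal hemorrhage or vitreous will not be included in the study". Section 3.11, on withdrawal, repeats the rule: images "not evaluable due to intravitreal hemorrhage or vitreous will not be included in the study". Sections 3.9 and 6.1 also limit the 900 patients to those with images of evaluable quality.

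Section 3.5 sets the reference standard: "Eye doctors (Normal, mtmDR, vtDR) make their decisions according to the ETDRS guidelines", by majority vote of three doctors. Its list of main signs ends with "IRMA, Neovascularization, Intravitreal hemorrhage, Preretinal hemorrhage". The same section requires that "the Specificity and Sensitivity values should be calculated separately for mtmDR and vtDR and each should be above 90" percent, and defines the overall measure as "Total correct number / Total number of eyes = Success rate".

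The only criterion that bears on diagnosability is in 3.4, where the primary endpoint asks the workflow "to diagnose 80% or more of the participants for more than mild diabetic retinopathy (mtmDR) and vision-threatening diabetic retinopathy (vtDR) separately". None of 3.5, 6.1 and Annex 1 says how an excluded or ungradable eye is counted.

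**The concern.** The exclusion names a sign that the protocol itself uses to grade the target disease. Corneal and lens opacity, in the same sentence of 3.10, are different because neither is on the 3.5 list. Patients already diagnosed with DR are excluded separately, so an eye lost through the hemorrhage rule belongs to an undiagnosed diabetic patient, the kind of person the software is meant to find.

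The rule also acts on images. Section 2.1 puts consent before photography, so an image can be found non-evaluable only after the participant has consented and been photographed. Nor does the rule say which images must be non-evaluable. Under 3.4 the software reads two non-mydriatic photographs per eye, while the doctors grade dilated four-quadrant photographs. Read literally, an eye that the doctors could grade as vtDR but the software could not read might be dropped.

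At stake is a mandatory success criterion. If such eyes are removed and the software would have failed on them, the reported vtDR sensitivity is too high for the population photographed, and the report would not show it.

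**Working it through.** **1. The plan's own figure.** Section 6.2 and Annex 1 give N = 778 for P0 = 0.90, P1 = 0.925 and one-sided alpha 0.05. The rejection boundary is 778 × 0.90 + 1.6449 × √(778 × 0.90 × 0.10) = 713.96, so H0 is rejected at 714 or more correct. Exact binomial alpha is 0.0530 and power 0.8004, both as printed. The sample size reproduces and is not in dispute. It concerns the overall success rate, whereas the exclusion acts on the vtDR sensitivity denominator.

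**2. Formula.** Let S be the sensitivity in retained vtDR eyes and f the share of all vtDR eyes removed.

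- Worst case, every removed eye missed: S(1 − f)
- Best case, every removed eye detected: S(1 − f) + f

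**3. Inputs.** The documents do not give f; 1% to 10% is assumed. S = 0.925 is borrowed from the highlighted row of 6.2 for illustration only.

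| f (assumed) | Worst case | Best case |
|---|---|---|
| 1% | 0.9158 | 0.9258 |
| 2% | 0.9065 | 0.9265 |
| 5% | 0.8788 | 0.9288 |
| 10% | 0.8325 | 0.9325 |

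**4. Tipping point.** The worst case falls below 0.90 when f > 1 − 0.90/S. This is 2.7% for S = 0.925 (1 − 0.90/0.925 = 0.0270) and 5.3% for S = 0.95 (1 − 0.90/0.95 = 0.0526).

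**5. Counts.** vtDR prevalence is not given. Assume 2%, 3% or 5% of 900 × 2 = 1,800 eyes, which is 36, 54 or 90 retained vtDR eyes. Starting from the smallest count above 90%:

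| Retained | One missed eye restored | Two restored |
|---|---|---|
| 33/36 = 91.7% | 33/37 = 89.2% | – |
| 49/54 = 90.7% | 49/55 = 89.1% | – |
| 82/90 = 91.1% | 82/91 = 90.1% (still passes) | 82/92 = 89.1% |

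These are borderline cases by construction. One more miss of any kind would also fail the first two. They show that few eyes can matter when vtDR is rare, not that hemorrhage eyes will decide this trial.

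**The case against.** The other side has a fair case, and much of it stands.

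- *A reader might infer that vtDR sensitivity is biased upward.* The documents do not support that as a fact. They do not say what EyeCheckup does with such images. If it flagged them all, removal would slightly lower the estimate, as the best-case column shows.
- *A reader might infer that the most severe vtDR eyes are all removed.* Only non-evaluable images go; eyes with hemorrhage that can still be graded stay in. Section 3.5 lists the sign without assigning it a grade, so target-positive status is probable, not stated.
- *A reader might see 3.5 and 3.10 as contradictory.* They are not, strictly: graders can look for hemorrhage in readable images while unreadable ones are excluded, and excluding ungradable images is common.
- *The population is already limited to eyes that can be imaged.* Section 3.1 confines the target population to people whose retinal image can be taken, and 3.9 and 3.10 exclude blur that prevents good photographs. For that population, part of the loss is one of generalisability and reporting. But a rule applied after consent and photography, and tied by name to a grading sign, still selects on disease.
- *The number may be very small.* Known DR and permanent visual impairment in either eye are exclusions. That is true, but vtDR eyes may be few for the same reason.
- *The 80% element covers unreadable eyes.* It does not return them to the sensitivity denominator, and its own denominator is unclear if they are deemed not in the study.
- *Deleting the exclusion would not be enough.* This is right. Section 3.5 has no ungradable category, so an eye the doctors cannot grade would still lack a reference result. The flow chart in 3.3 lists dilated ophthalmoscopy, but no section makes it part of the reference standard. The fix has to treat such eyes separately.

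**Conclusion.** The point holds as a gap in counting and reporting. Followed as written, the plan can drop eyes because of a sign of the target disease, and no section requires them to be counted, reported or bounded. vtDR sensitivity can then be overstated, on condition that EyeCheckup would miss these eyes or return no result.

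The size cannot be computed from the documents. It rests on three unknowns: the number of vtDR eyes, the share removed, and the software's output on them. With an assumed S of 0.925, the 90% threshold is lost once more than about 2.7% of vtDR eyes are removed and all would have been missed. With 10% removed, all-eyes sensitivity could lie anywhere from 0.8325 to 0.9325. Should-fix, moderate confidence.

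**What to change.** Reconcile 3.10 and 3.11, and the matching evaluable-quality wording in 3.9 and 6.1, with 3.5, so that a consented, photographed eye is not removed from the analysis because of intravitreal hemorrhage. Then state in 3.5, 6.1 and Annex 1, before the data are analysed:

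1. Where the doctors can grade the dilated images, the eye stays in. If their grade is vtDR, an EyeCheckup 'no result' counts as not detected.
2. Where the doctors cannot grade the images, the eye is counted and reported by cause, and vtDR sensitivity is given with best-case and worst-case bounds. With TP detected among n graded vtDR eyes and u such eyes all taken as vtDR, these are (TP + u)/(n + u) and TP/(n + u).
3. Sensitivity without the hemorrhage eyes is reported as a secondary figure.
4. The denominator of the 80% diagnosability element in 3.4 includes these eyes.

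The cost is wording in several sections and a modest amount of analysis, with no additional patients, readers or photographs. The downside is that the reported vtDR sensitivity may be slightly lower.

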3.11. Withdrawal of Volunteers from the Study - Exclusion Criteria

The volunteer may withdraw from this study at any time without giving any reason, provided that the principal investigator/doctor is informed. He assumes no liability for his refusal or subsequent withdrawal from this study, and this does not in any way affect the medical care that the patient needs now or in the future.

The researcher/doctor or the supporting organization, who is the coordinator of the study, may exclude the subject from the study without the consent of the subject, due to their negligence in fulfilling the requirements of the study program or in order to improve the quality of the medical care received by the patient. Fundus images that have corneal or lens opacification that will prevent imaging, and that are not evaluable due to intravitreal hemorrhage or vitreous will not be included in the study. Patients already diagnosed with DR will not be included in the study.

[figure not shown]
Participants withdrawing from the study for a serious or non-serious ACE should be monitored by the investigator until the clinical outcome of the ADE is determined. Any participant experiencing an ADE may withdraw from the study at any time at the discretion of the investigator. ADE(s) should be noted with appropriate ORFs and participant progress should be monitored until the ADE is resolved. The medical monitor or project manager should be informed.

4. STUDY TREATMENTS

4.1. Route of administration, dosage, dosing regimen, and Duration of Treatment of Subjects

No intervention will be made to the body. Since the medical device is software, there will be no drug use and no dosage. Pupil dilatation will be provided by instilling 1-2 drops of Tropicamide drops into both eyes to enlarge the pupil. Since tropicamide drops are eye drops that are always used during routine eye examinations, they will not be considered a drug intervention in a clinical study. The processing time is equal to the growth time of the pupil and the time to obtain 2 images from both eyes from the fundus camera. While it takes about 20-30 minutes for the pupils to grow, it takes 1-2 minutes for the photos to be taken. These procedures are not the application of the EyeCheckup product to the patient; It is the process of obtaining retinal images with the standard method using CE-marked eye drops and a CE-marked fundus camera.

There is no follow-up period, as no follow-up is required for the patient whose fundus image was taken. Since the device is not used for treatment purposes, there is no treatment period. For the patient with any finding in their eyes, a referral is made to the doctor. This process is advanced by the doctor.

4.2. Drugs Not Allowed Before And/or After Research

There are no drugs or treatments that are required or are not authorized prior to the trial. Since only fundus images of the patient will be used, there is no drug use that will affect image acquisition. Before image acquisition, only 1-2 drops of Tropicamide will be instilled into the eye.

There is no drug or treatment application after the fundus image is taken.

4.3. Volunteer Compliance Monitoring Methods

Follow-up and treatment of volunteers after fundus photography is not planned. The study will continue through the photographs obtained from the volunteer.

5. RELIABILITY STATEMENT

5.1. Device Reliability Assessment

Ongoing safety monitoring will be performed by the responsible person who will regularly review reported adverse effects (AEs) or unexpected adverse device effects (UADEs) from the clinical trial site and promptly report them to the sponsor.

5.2. Adverse device effect (ADE)

Adverse device effect (ADE) means an adverse event associated with the use of an investigational medical device.

All adverse events that are suspected, observed, or voluntarily reported causally related to the study will be recorded on the adverse event page of the electronic case report form.

5.3. Unexpected Adverse Device Effects (UADE)

Unexpected adverse device effect (UADE) is any serious adverse effect on health or safety, or any life-threatening problem or death, resulting from or associated with its use, not previously identified in nature, severity, or extent.

[figure not shown]
UADEs occurring on the visit will be monitored to adequately assess the participant's safety or until the event has stabilized. When the case is resolved, a resolution date should be written on the case report form. All UADEs will be followed up until resolution or until the participant is medically stable. All adverse events that are suspected, observed or voluntarily reported causally related to the study will be recorded on the adverse event page of the case report form, then entered into the electronic data capture (EDC) system.

5.4. Adverse device effect notification - Unexpected Adverse Device Effects notification

"Adverse Device Effect" notification will be made to the Ministry and Ethics Committees in accordance with the provisions of the relevant legislation.

All recordable ADEs will be entered into the security data system within 7 days of identification. Recordable UADEs will be entered into the data system within 24 hours of identification. If there

EC-2021DR-TR DETECTION AND CLASSIFICATION OF DIABETIC RETINOPATHY FROM POSTERIOR POLE IMAGES WITH A DEEP LEARNING MODEL

are any technical difficulties, UADE will be notified by telephone or fax communication. This data will be entered into the electronic data capture (EDC) system as soon as the system is available.

6. STATISTICS

6.1. Analysis

Fundus images of 900 volunteer patients with evaluable quality, with or without pathology, who applied to Akdeniz University Endocrinology and Metabolism Diseases Department with the diagnosis of diabetes, were not diagnosed with Diabetic Retinopathy before, and whose images can be obtained from the posterior polar region of the eye with a fundus camera, will be included in the study, which will be carried out as a single-center study. The sample size was determined by Akdeniz University Statistics Consultancy Application and Research Center, taking into account the incidence of diabetic retinopathy in diabetic patients. Upon confirmation that the Al algorithm is working successfully, the trial will be terminated when the intended number of 900 patients is reached. The success criterion of the study is specified in Article 3.5.

The classification performance of the AI algorithm will be evaluated with reference to the diagnosis made by the doctors. Gold standard test results will be obtained based on the diagnosis from three different doctors. At this stage, the compatibility between the diagnosis from the doctors will be evaluated according to the Kappa statistics, and the similarity of the decisions made by the doctors with each other will be examined. The diagnoses of the patients will then be evaluated together with the results of the AI algorithm, and performance measures of the AI algorithm (sensitivity, selectivity, positive predictive value, negative predictive value, overall accuracy, etc.) will be obtained. Whether the performances of the AI algorithm are clinically acceptable or not will be evaluated with ratio tests (single sample population ratio significance test, Fisher Exact test, Chi-square tests, etc.) according to the threshold values to be determined by experts. A data analysis software will be selected among various software (R, SPSS, TURCOSA, Stata, etc.) to do the statistical analysis in accordance with the purpose. For statistical analysis, the level of significance will be taken as 0.05. (Annex-1 Analysis Plan)

